14.1.3.2 Time to event variables

14.1.3.2.1 Progression-free survival

Usually in all Oncology studies, patients are followed for tumor progression after discontinuation of study medication for reasons other than progression or death. If this is not used, e.g. in Phase I or II studies, this should be clearly stated in the protocol. Note that randomized trials (preferably blinded) are recommended where PFS is to be the primary endpoint.

Progression-free survival (PFS) is the time from date of randomization/start of treatment to the date of event defined as the first documented progression or death due to any cause. If a patient has not had an event, progression-free survival is censored at the date of last adequate tumor assessment.

14.1.3.2.2 Overall survival

All patients should be followed until death or until patient has had adequate follow-up time as specified in the protocol whichever comes first. The follow-up data should contain the date the patient was last seen alive / last known date patient alive, the date of death and the reason of death (“Study indication” or “Other”).

Overall survival (OS) is defined as the time from date of randomization/start of treatment to date of death due to any cause. If a patient is not known to have died, survival will be censored at the date of last known date patient alive.

14.1.3.2.3 Time to progression

Some studies might consider only death related to underlying cancer as an event which indicates progression. In this case the variable “Time to progression” might be used. TTP is defined as PFS except for death unrelated to underlying cancer.

Time to progression (TTP) is the time from date of randomization/start of treatment to the date of event defined as the first documented progression or death due to underlying cancer. If a patient has not had an event, time to progression is censored at the date of last adequate tumor assessment.

14.1.3.2.4 Time to treatment failure

This endpoint is often appropriate in studies of advanced disease where early discontinuation is typically related to intolerance of the study drug. In some protocols, time to treatment failure may be considered as a sensitivity analysis for time to progression. The list of discontinuation reasons to be considered or not as treatment failure may be adapted according to the specificities of the study or the disease.

Time to treatment failure (TTF) is the time from date of randomization/start of treatment to the earliest of date of progression, date of death due to any cause, or date of discontinuation due to reasons other than ‘Protocol violation’ or ‘Administrative problems’. The time to treatment failure for patients who did not experience treatment failure will be censored at last adequate tumor assessment.

14.1.3.2.5 Duration of response

The analysis of the following variables should be performed with much caution when restricted to responders since treatment bias could have been introduced. There have been reports where a treatment with a significantly higher response rate had a significantly shorter duration of response but where this probably primarily reflected selection bias which is explained as follows: It is postulated that there are two groups of patients: a good risk group and a poor risk group. Good risk patients tend to get into response readily (and relatively quickly) and tend to remain in response after they have a response. Poor risk patients tend to be difficult to achieve

a response, may have a longer time to respond, and tend to relapse quickly when they do respond. Potent agents induce a response in both good risk and poor risk patients. Less potent agents induce a response mainly in good risk patients only. This is described in more detail by [Morgan \(1988\)](#).

It is recommended that an analysis of all patients (both responders and non-responders) be performed whether or not a “responders only” descriptive analysis is presented. An analysis of responders should only be performed to provide descriptive statistics and even then interpreted with caution by evaluating the results in the context of the observed response rates. If an inferential comparison between treatments is required this should only be performed on all patients (i.e. not restricting to “responders” only) using appropriate statistical methods such as the techniques described in [Ellis et al \(2008\)](#). It should also be stated in the protocol if duration of response is to be calculated in addition for unconfirmed response.

For summary statistics on “responders” only the following definitions are appropriate. (Specific definitions for an all-patient analysis of these endpoints are not appropriate since the status of patients throughout the study is usually taken into account in the analysis).

Duration of overall response (CR or PR): For patients with a CR or PR (which may have to be confirmed the start date is the date of first documented response (CR or PR) and the end date and censoring is defined the same as that for time to progression.

The following two durations might be calculated in addition for a large Phase III study in which a reasonable number of responders is seen.

Duration of overall complete response (CR): For patients with a CR (which may have to be confirmed) the start date is the date of first documented CR and the end date and censoring is defined the same as that for time to progression.

Duration of stable disease (CR/PR/SD): For patients with a CR or PR (which may have to be confirmed) or SD the start and end date as well as censoring is defined the same as that for time to progression.

14.1.3.2.6 Time to response

Time to overall response (CR or PR) is the time between date of randomization/start of treatment until first documented response (CR or PR). The response may need to be confirmed depending on the type of study and its importance. Where the response needs to be confirmed then time to response is the time to the first CR or PR observed.

Although an analysis on the full population is preferred a descriptive analysis may be performed on the “responders” subset only, in which case the results should be interpreted with caution and in the context of the overall response rates, since the same kind of selection bias may be introduced as described for duration of response in [Section 14.1.3.2.5](#). It is recommended that an analysis of all patients (both responders and non-responders) be performed whether or not a “responders only” descriptive analysis is presented. Where an inferential statistical comparison is required, then all patients should definitely be included in the analysis to ensure the statistical test is valid. For analysis including all patients, patients who did not achieve a response (which may have to be a confirmed response) will be censored using one of the following options.

- at maximum follow-up (i.e. FPFV to LPLV used for the analysis) for patients who had a PFS event (i.e. progressed or died due to any cause). In this case the PFS event is the worst possible outcome as it means the patient cannot subsequently respond. Since the statistical analysis usually makes use of the ranking of times to response it is sufficient to assign the worst possible censoring time which could be observed in the study which is equal to the maximum follow-up time (i.e. time from FPFV to LPLV)
- at last adequate tumor assessment date otherwise. In this case patients have not yet progressed so they theoretically still have a chance of responding

Time to overall complete response (CR) is the time between dates of randomization/start of treatment until first documented CR. Similar analysis considerations including (if appropriate) censoring rules apply for this endpoint described for the time to overall response endpoint.

14.1.3.2.7 Definition of start and end dates for time to event variables

Assessment date

For each assessment (i.e. evaluation number), the **assessment date** is calculated as the latest of all measurement dates (e.g. X-ray, CT-scan) if the overall lesion response at that assessment is CR/PR/SD/UNK. Otherwise - if overall lesion response is progression - the assessment date is calculated as the earliest date of all measurement dates at that evaluation number.

Start dates

For all “time to event” variables, other than duration of response, the randomization/ date of treatment start will be used as the start date.

For the calculation of duration of response the following start date should be used:

- Date of first documented response is the assessment date of the first overall lesion response of CR (for duration of overall complete response) or CR / PR (for duration of overall response) respectively, when this status is later confirmed.

End dates

The end dates which are used to calculate ‘time to event’ variables are defined as follows:

- Date of death (during treatment as recorded on the treatment completion page or during follow-up as recorded on the study evaluation completion page or the survival follow-up page).
- Date of progression is the first assessment date at which the overall lesion response was recorded as progressive disease.
- Date of last adequate tumor assessment is the date the last tumor assessment with overall lesion response of CR, PR or SD which was made before an event or a censoring reason occurred. In this case the last tumor evaluation date at that assessment is used. If no post-baseline assessments are available (before an event or a censoring reason occurred) the date of randomization/start of treatment is used.
- Date of next scheduled assessment is the date of the last adequate tumor assessment plus the protocol specified time interval for assessments. This date may be used if back-dating

is considered when the event occurred beyond the acceptable time window for the next tumor assessment as per protocol (see [Section 14.1.3.2.8](#)).

Example (if protocol defined schedule of assessments is 3 months): tumor assessments at baseline - 3 months - 6 months - missing - missing - PD. Date of next scheduled assessment would then correspond to 9 months.

- Date of discontinuation is the date of the end of treatment visit.
- Date of last contact is defined as the last date the patient was known to be alive. This corresponds to the latest date for either the visit date, lab sample date or tumor assessment date. If available, the last known date patient alive from the survival follow-up page is used. If no survival follow-up is available, the date of discontinuation is used as last contact date.
- Date of secondary anti-cancer therapy is defined as the start date of any additional (secondary) antineoplastic therapy or surgery.

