7.1.5 Follow-up period

Safety Follow-up

All patients must have safety evaluations until 150 days after the last dose of PDR001 or 90 days after the last dose of MCS110 (whichever the longer). The 30-, 90- and 150-day safety follow-up can be done by telephone call or visit.

Concomitant medications will be collected until the 30-day safety follow-up has been completed or the start of a new antineoplastic therapy, whichever occurs first.

Data collected should be added to the Adverse Events CRF, the antineoplastic therapies since discontinuation of study treatment CRF, and the Concomitant Medications CRF.

For a female participant of child bearing potential, a pregnancy test will be performed on a monthly basis after stopping the study treatment ([Section 7.2.2.5.7](#)).

For patients who transfer to another clinical study to continue provision of study treatment or an alternative treatment option, as described in [Section 4.3](#), the follow-up for safety will not be performed. For all other patients, the safety evaluation period will be completed but the disease-progression and survival follow up will not be performed.

Disease progression follow-up period

Patients who discontinue study treatment for any reason other than death, disease progression per irRC, lost to follow-up, consent withdrawal, start of new cancer therapy or study

termination, should return for tumor evaluation assessments every 9 weeks until 51 weeks, then every 12 weeks until progression of disease per irRC, withdrawal of consent, lost to follow-up ([Section 7.2.1](#)), or until the end of the study is reached as described in [Section 4.3](#).

If patients refuse to return for these visits or are unable to do so, every effort should be made to contact them or a knowledgeable informant by telephone to determine if the patient had disease progression.

For patients who transfer to another clinical study or an alternative treatment option to continue provision of study treatment, the follow-up for disease progression will not be performed.

Survival follow-up period

Upon completion of the safety follow-up and disease progression follow-up (if applicable), all patients enrolled in the Phase Ib and Phase II parts will be followed for survival every 3 months (can be done by telephone call) until death or until the end of the study is reached, as described in [Section 4.3](#), unless they withdraw consent or are lost to follow-up.

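### The overall-survival censoring date is defined two conflicting ways; taken literally, one of them censors living off-treatment patients at the end-of-treatment visit and biases Kaplan-Meier OS downward.

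*Protocol*

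**What the plan says.** Protocol Appendix 1, section 14.1.3.2.2, sets the general rule: "If a patient is not known to have died, survival will be censored at the date of last known date patient alive".

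Section 14.1.3.2.7 then defines the date of last contact in one bullet that makes three statements:

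- It marks the most recent point at which the patient was still confirmed living, and the bullet says how to find it: "This corresponds to the latest date for either the visit date, lab sample date or tumor assessment date".
- A survival follow-up page, if there is one, supplies the date.
- "If no survival follow-up is available, the date of discontinuation is used as last contact date".

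An earlier bullet in the same list fixes the meaning of the last term: "Date of discontinuation is the date of the end of treatment visit". For deaths, the list accepts dates "during follow-up as recorded on the study evaluation completion page or the survival follow-up page", so a death after treatment counts even when there is no survival page.

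The schedule is in Protocol 7.1.5. "All patients must have safety evaluations until 150 days after the last dose of PDR001" (or 90 days after the last MCS110 dose, whichever is longer), and "The 30-, 90- and 150-day safety follow-up can be done by telephone call or visit". Patients who stop without irRC progression are also scanned every 9, later every 12, weeks. The survival paragraph opens "Upon completion of the safety follow-up and disease progression follow-up (if applicable), all patients enrolled in the Phase Ib and Phase II parts" and then provides for contact every 3 months.

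SAP 2.7.2 plans a Kaplan-Meier median OS with a 90% CI, where applicable. SAP 2.7.3 has a censoring rule for PFS and none for OS.

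**The concern.** The bullet gives two answers for the same patient. Take someone who stopped treatment four months before the data cut, has had the day-30 and day-90 safety contacts and is alive. The general rule and the opening of the bullet point to a date after EOT, provided the contact or a scan supplies one. The closing sentence points to EOT. The SAP does not choose.

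The choice matters because the closing sentence treats deaths and survivors differently. A patient who dies three months after EOT is an event at three months. A patient known alive at that time, but without a survival page, leaves the risk set at EOT. Events are counted over a window from which part of the living exposure has been removed, so the hazard in that window is overstated and the survival curve is too low.

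The affected group follows from the schedule. Anyone off treatment and still in the 150-day safety period, or still in progression follow-up, cannot yet have reached survival follow-up. The end-of-study wording in 7.1.5 also describes patients who complete safety follow-up with no survival follow-up afterwards.

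**Working it through.** **Is there a planned figure to reproduce?** No. Neither document states an assumed OS, an event count or a precision target for OS, so size can only be shown under stated assumptions.

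**Inputs from the documents**

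- Last patient enrolled 10-Jan-2019 (Amendment 05, study status).
- Primary analysis once all patients have completed six cycles or discontinued (Protocol 10.4.2.2): 6 × 21 = 126 days, so about 16-May-2019.
- Safety contacts at days 30, 90 and 150; survival contacts every 3 months after that (7.1.5).
- Status at 08-Jul-2019: 141 treated, 6 on treatment, 41 in survival follow-up. The other 141 − 6 − 41 = 94 are not broken down into dead, off study or in earlier follow-up, so the number without a survival page cannot be read off.

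**Assumptions not in the documents**

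- Uniform accrual over 275 days (10-Apr-2018 to 10-Jan-2019).
- Exponential time on treatment (median 2 or 4 months) and exponential survival after it (median 3, 6 or 9 months).
- First survival page 150 or 240 days after EOT.
- All deaths up to the cut-off are known.
- Patients still on treatment are censored at the cut-off under every rule.

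**Method.** Kaplan-Meier on 400,000 simulated patients per scenario, with three censoring dates for living off-treatment patients: (a) the cut-off, vital status known; (b) the last actual contact; (c) EOT if there is no survival page, otherwise the last contact. Four of the twelve scenarios:

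| On treatment / after (median, months) | First survival page | Under fallback | 6-month OS, a / b / c | 9-month OS, a / b / c | Median (months), a / b / c |
|---|---|---|---|---|---|
| 2 / 3 | 150 d | 16.6% | 50.4 / 48.9 / 46.3% | 28.8 / 25.3 / 22.6% | 6.06 / 5.90 / 5.64 |
| 2 / 6 | 150 d | 22.9% | 69.1 / 67.7 / 65.2% | 51.1 / 46.7 / 43.5% | 9.20 / 8.53 / 8.06 |
| 2 / 6 | 240 d | 37.2% | 69.2 / 67.8 / 59.9% | 51.3 / 46.9 / 36.9% | 9.23 / 8.55 / 7.18 |
| 4 / 6 | 150 d | 24.3% | 79.4 / 78.8 / 77.5% | 64.2 / 61.8 / 59.3% | 12.04 / 10.91 / 10.43 |

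The loss under (c) in row 1 is 50.4 − 46.3 = 4.1 points at 6 months and 28.8 − 22.6 = 6.2 at 9 months. In row 3 it is 69.2 − 59.9 = 9.3 and 51.3 − 36.9 = 14.4.

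Over all twelve scenarios, 17 to 44% of patients fall under the fallback, and the estimate is low by about 2 to 9 points at 6 months and 4 to 14 at 9 months. Rule (a) recovers the true curve. Rule (b) lies between (a) and (c) in every scenario.

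**Second model.** Exponential OS with a median of 180 to 270 days, the same contacts and cut-off, and the first survival page at 150 days: 16 to 21% fall under the fallback, with a loss of about 4 points at 6 months and 6 to 7 at 9 months. For a true median of 180 days, the estimated medians are 162 days under (c), 173 under (b) and 179 under (a). A repeat with median time on treatment set at 61 or 91 days gave 15 to 20%, 3 to 4 points and 6 to 7 points.

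**The case against.** **The closing sentence may be only a last resort.** The general OS rule and the start of the bullet both say last known alive, and tumour assessments are named outright, so a patient still being scanned need not go back to EOT. This stands. A reader might infer that the plan settles on EOT for everyone without a survival page; the documents support a contradiction, not a settled rule.

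**Appendix 1 is a generic sponsor guideline.** It expects study-level adaptation, and SAP section 1 places derivations in a programming specification that is not available here. This also stands: the derivation actually used is unknown. But no rule in the protocol or SAP overrides the sentence.

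**The effect is small beside the noise.** With 20 patients, the 90% half-width for a 6-month OS near 50% is 1.645 × √(0.5 × 0.5 / 20) ≈ 18 points. OS is descriptive and untested. That limits the consequence. However, the shift is systematic and in one direction, so a reader of the interval cannot allow for it.

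**The problem may be confined to the primary report.** The first end-of-study route in Protocol 4.3 requires safety follow-up to be complete, so the safety-window mechanism bears mainly on the primary CSR. That is right, although early termination or transfer could still leave patients without a survival page.

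**Conclusion.** The point holds as an unresolved contradiction with a predictable consequence. Appendix 1 gives two incompatible dates for last contact, and the SAP does not choose. If the closing sentence is applied at the primary cut-off, Kaplan-Meier OS is biased downward. The direction was the same in every scenario run. The size is not fixed by the documents: the 4-point and 6-to-7-point figures depend on the assumed survival, accrual and timing of the first survival page.

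Four stronger readings are tempting and unsupported:

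- That every OS estimate is lowered. A group with nobody under the fallback is unaffected, and early time points barely move.
- That the patients doing best lose exposure. Those still on treatment, and those with a survival page, are not touched.
- That censoring at the last safety contact removes the bias. Contacts are intermittent, so part remains (173 against 179 days in the 180-day case).
- That all the needed dates are already collected. Protocol 7.1.5 sends safety follow-up data to the adverse event, antineoplastic therapy and concomitant medication forms and names no field for the date of an uneventful call. Table 7-1 does list safety follow-up among the visits, so a date may exist; the documents do not settle it.

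ORR, CBR, the expansion decisions and the sample sizes do not depend on this rule.

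**What to change.** Add an OS rule to SAP 2.7.3: a patient not known to have died is censored at the latest date known alive from any collected source (visit, safety contact including by telephone, scan, laboratory sample, survival page). State that this supersedes the closing sentence of the last-contact bullet in Appendix 1, and align the programming specification with it.

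Confirm before database lock that the date of a telephone safety contact with nothing to report is captured. If it is not, the rule loses part of its value for patients in the safety window.

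To remove the remaining bias, check vital status at the data cut-off for patients in follow-up, where consent and the end-of-study provisions allow.

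The first change costs a paragraph of SAP text and one derivation. The second is a check of the data collection forms. The third asks sites for one status update per patient concerned and is the only part with operational cost.

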14.1.3.2.8 Handling of patients with non-measurable disease only at baseline

It is possible that patients with only non-measurable disease present at baseline are entered into the study, either because of a protocol violation or by design (e.g. in Phase III studies with PFS as the primary endpoint). In such cases the handling of the response data requires special consideration with respect to inclusion in any analysis of endpoints based on the overall response evaluations.

It is recommended that any patients with only non-measurable disease at baseline should be included in the main (ITT) analysis of each of these endpoints.

Although the text of the definitions described in the previous sections primarily relates to patients with measurable disease at baseline, patients without measurable disease should also be incorporated in an appropriate manner. The overall response for patients with measurable disease is derived slightly differently according to [Table 14-4](#).

Table 14-4 Overall lesion response at each assessment: patients with non-target disease only

Non-target lesions	New Lesions	Overall lesion response
CR	No	CR
Non-CR/Non-PD ¹	No	Non-CR/non-PD
UNK	No	UNK
PD	Yes or No	PD
Any	Yes	PD

¹ As defined in [Section 14.1.2.4](#)

In general, the **non-CR/non-PD response** for these patients is considered equivalent to an SD response in endpoint determination. In summary tables for best overall response patients with only non-measurable disease may be highlighted in an appropriate fashion e.g. in particular by displaying the specific numbers with the non-CR/non-PD category.

In considering how to incorporate data from these patients into the analysis the importance to each endpoint of being able to identify a PR and/or to determine the occurrence and timing of progression needs to be taken into account.

For ORR it is recommended that the main (ITT) analysis includes data from patients with only non-measurable disease at baseline, handling patients with a best response of CR as “responders” with respect to ORR and all other patients as “non-responders”.

For PFS, it is again recommended that the main ITT analyses on these endpoints include all patients with only non-measurable disease at baseline, with possible sensitivity analyses which exclude these particular patients. Endpoints such as PFS which are reliant on the determination and/or timing of progression can incorporate data from patients with only non-measurable disease.

